12 CONFLICT OF INTEREST

Any investigator and/or research staff member who has a conflict of interest with this study (such as patent ownership, royalties, or financial gain greater than the minimum allowable by their institution) will fully disclose the nature of the conflict of interest.

13 DATA OWNERSHIP

The investigators participating in the study are the owners of the data resulting therefrom. All centers and investigators participating in the study are invited not to disseminate information or data without prior express agreement with the Study Coordinator and Principal Investigators.

Protocol code: REBUC
Effective date: 03/10/2022
Version no: 4.0
Page 31 / 50

14 PUBLICATION POLICY

After completion of the study, the Study Coordinator will prepare a draft manuscript containing final results of the study on the basis of the statistical analysis. The manuscript will be derived to the co-authors for comments and after revision will be sent to the appropriately selected peer-reviewed scientific journal. All information concerning this study has to be treated confidentially. In all publication/s the confidentiality of patients’ data will be ensured.

All publications, abstracts, presentations, manuscripts and slides including data from the present study will be submitted to and reviewed by the Study Coordinator for coordination and homogeneity purposes. By signing this study protocol, the investigators accept that the results of this study can be presented to national and international authorities. They also accept that in this context their name, address, qualification and grade of involvement in the trial will be published.

The Study Coordinator will be the Senior Author and the Corresponding Author of the relevant publication/s. The Authors’ list will include all the investigators (up to the maximum required by the Journal to whom the article will be submitted) in a decreasing order of patients included into the final analysis for the primary outcome, as well as the study statistician.

The funding body will be acknowledged within the publication/s, but they do not have any review and publication right on the data from the study, including their timelines for doing so.

It is responsibility of the Study Coordinator to notify the Principal Investigators of the outcome of the study by provision of the publication/s.

15 Study time table (Gantt chart)

The whole study duration is 36 months, while the time frame from the enrolment of the first patient is 32 months. The patients’ participation consists of a 3 weeks screening period, one week to undergo endoscopy with mucosal sampling and peripheral blood harvest, a 6 months mandatory follow-up period, a 6 further months of facultative follow-up period, and a 4 weeks end of study visit. Thus, the recruitment period lasts 29 months and the minimum expected duration of subject participation is of 7 months. The whole study duration is 36 months, and the subdivision of the activities by trimesters and by involved units is represented here below:

Task	I	II	III	IV	V	VI	VII	VIII	IX	X	XI	XII
1a												
1b												

Protocol code: REBUC
Effective date: 03/10/2022

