Data will be described with the mean and standard deviation or the median and 25th-75th percentiles if continuous and as counts and percent if categorical. For the primary endpoint we will compute the prevalence as the ratio of the number of patients diagnosed with EBV infection to the number of patients evaluated, together with its 95%CI. We will use the Fisher exact test to compare the prevalence in UC patients to that of control. We will use binomial regression models to adjust for potential confounders. We will compute sensitivity, specificity, area under the ROC curve and predictive values with 95%CIs. We will use the Spearman R and the Fisher exact test to assess the association, for continuous and categorical independent variables, respectively, with dependent variables. We will use Cox regression to assess the association of EBV infection with colectomy and of hospitalization for any cause; we will use Poisson regression to assess the association of EBV infection with the number of hospitalization from any cause. We will use Stata 17 or later versions for computations. A 2-sided p-value <0.05 will be considered statistically significant. We will apply the Bonferroni correction for post-hoc comparisons.

Ethical considerations

The protocol and its annexes are subject to review and approval by the competent Independent Ethics Committee(s). Each patient and control gives written informed consent after approval by the local Ethics Committee is obtained. Both the Principal Investigators and the Study Coordinator will ensure that this study is conducted in agreement with either the Declaration of Helsinki and the Italian laws and regulations.

Study time table

[figure not shown]
Project starting date: 30.10.2022

Project completion of data collection: 30.05.2025

Project data analysis: 31.07.2025

Project presentation of scientific report: 30.10.2025

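### The recruitment and follow-up periods do not fit the study dates: late-entering active UC patients cannot complete the mandatory 6-month follow-up before data collection closes

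*Protocol*

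**What the plan says.** The protocol gives its timetable in two places.

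Section 15 (Study time table) gives durations. On the overall length: "The whole study duration is 36 months, while the time frame from the enrolment of the first patient is 32 months". Each patient's participation is made up of "a 3 weeks screening period, one week to undergo endoscopy with mucosal sampling and peripheral blood harvest", followed by "a 6 months mandatory follow-up period, a 6 further months of facultative follow-up period, and a 4 weeks end of study visit". It then concludes: "Thus, the recruitment period lasts 29 months and the minimum expected duration of subject participation is of 7 months".

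The Summary (Study time table) gives calendar dates: "Project starting date: 30.10.2022", "Project completion of data collection: 30.05.2025" and "Project data analysis: 31.07.2025". The scientific report is dated 30.10.2025.

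Follow-up differs by group. Section 6 and Appendix 3 schedule visits at 3 and 6 months (mandatory) and at 9 and 12 months (optional) for active UC. Appendix 4 gives UC in remission and IBS subjects screening and baseline only. Section 6 sets the longitudinal aim at 6 months. Section 5.2.2, item i, makes the 6- and 12-month outcome (colectomy, number and cause of hospitalisations) a secondary endpoint.

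**The concern.** The recruitment period and the minimum participation add up to the whole 36-month study. They do not fit the 32 months from first enrolment given in the same section, nor the date on which the Summary says data collection is complete. If both timetables are followed as written, recruitment stays open to active UC patients whose 6-month visit falls after the data are closed.

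The 6-month outcome of those patients would then be cut short by the calendar and not by anything that happened to them. This loss comes on top of the 10% drop-out expected in section 10, item n. That item also carries forward the last observation when a follow-up clinical assessment is missing, and says that outcome cannot be evaluated if clinical, endoscopic and histologic data are missing by month 12. Gaps created by the timetable would fall under these rules unless the dates are put right.

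**Working it through.** **Inputs.** From section 15: study duration 36 months; frame from first enrolment 32 months; recruitment 29 months; minimum participation 7 months; components of 3 weeks, 1 week and 6 months. From the Summary: start 30.10.2022, data collection complete 30.05.2025, analysis 31.07.2025, report 30.10.2025.

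**1. The plan's own figures.** 3 weeks + 1 week + 6 months = 6.9 months, which rounds to the stated 7. And 36 - 7 = 29, the stated recruitment period. Both are reproduced. The 29 months were evidently obtained by subtracting participation from the whole study, which leaves no time for cleaning, analysis and reporting.

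**2. Dates as months from 30.10.2022.** Data collection closes at month 31, analysis is at month 33 and the report at month 36.

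**3. Check inside section 15.** 29 + 7 = 36, against 32 months from first enrolment: 4 months too long. A patient enrolled at month 29 has 32 - 29 = 3 months left, not 7.

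**4. Check against the Summary.** Start + 29 months = 30.03.2025. Adding 6 months gives 30.09.2025, which is 4 months after data collection closes and 2 months after the analysis date. Adding the full 7 months gives 30.10.2025, the date of the report.

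**5. Size of the shortfall.** Latest workable entry = cut-off - time required. Shortfall = 29 - latest workable entry. Share = shortfall / 29, assuming uniform accrual from month 0. The time required is 6 months if entry is counted from baseline and 7 if it is counted from the start of screening.

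| Cut-off | Time required | Latest entry | Shortfall | Share |
|---|---|---|---|---|
| Data collection, month 31 | 6 months | month 25 | 4 months | 4/29 = 14% |
| Data collection, month 31 | 7 months | month 24 | 5 months | 5/29 = 17% |
| 32-month frame | 6 months | month 26 | 3 months | 3/29 = 10% |
| 32-month frame | 7 months | month 25 | 4 months | 4/29 = 14% |
| Analysis, month 33 | 6 months | month 27 | 2 months | 2/29 = 7% |
| Analysis, month 33 | 7 months | month 26 | 3 months | 3/29 = 10% |
| End of study, month 36 | 7 months | month 29 | 0 | 0% |

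Only the last row fits, and it requires data collection to run to the day of the report, against the Summary.

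**6. Later first enrolment.** If the 32-month frame means that the first patient enters at month 36 - 32 = 4, recruitment ends at month 4 + 29 = 33, after data collection has closed. The shortfall is then 33 - 25 = 8 to 33 - 24 = 9 months, or 8/29 = 28% to 9/29 = 31%.

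**7. In patients.** The protocol does not state how many of the 100 UC patients will have active disease. Assuming 30 to 100, the 14-17% corresponds to about 30 × 4/29 = 4 up to 100 × 5/29 = 17 patients.

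**The case against.** Several points on the other side stand.

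- Only active UC patients have scheduled follow-up. For UC in remission and IBS, entry at month 29 plus about one month of screening and endoscopy is complete before month 31.
- The primary endpoint is prevalence at baseline, and the sample size rests on it alone. A reader might infer that the study's main result is at risk. It is not.
- Section 8.2 analyses colectomy and hospitalisation by Cox regression. A patient cut off at data close is censored and still contributes follow-up time, so the information is truncated and not wholly lost. The number of hospitalisations and the missing-data rules of section 10 remain exposed.
- Enrolment is also limited by a target of about 100 UC patients. If that is reached by month 24-25, nobody is affected. But the protocol states 29 months and sets no earlier close for active UC.
- The shading of the Gantt chart is not legible in the text available and may show the intended sequence. It cannot remove the conflict between the written durations and dates.

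Two stronger readings should be resisted. By the same arithmetic, 10 to 11 of 29 months (34-38%) enter too late for 12 months by month 31, and a reader might infer that a third or more of the 12-month data will be missing. That follow-up is optional and covers only patients selected by medical judgement, so the figure does not describe the planned 12-month data. A reader might also add the 4-week end-of-study visit, obtain about 7.8 months and call the stated 7 a miscalculation. The 7 is given as a minimum, and the other mandatory components reproduce it. Appendix 3 shows no visit after the 6-month column on the mandatory schedule, and the 4 weeks may be a visit window.

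**Conclusion.** The two timetables contradict each other, and section 15 contradicts itself: 36 months are needed, against 32 from first enrolment and 31 to the close of data collection. Active UC patients who enter in roughly the last 4 to 5 recruitment months cannot complete the mandatory 6-month follow-up in time. That is about 14-17% of active UC patients under uniform accrual from the project start, and 28-31% if the first patient enters at month 4. Neither accrual pattern is stated in the protocol, so the shares are illustrative; the contradiction in dates does not depend on them. The damage is confined to secondary endpoint i. The dates should be corrected, but the primary analysis is not in question.

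**What to change.** Reconcile section 15 with the Summary so that one set of dates applies throughout. There are two ways.

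- **Keep the data-collection date.** End entry of active UC patients by month 24 (30.10.2024) if the full 7 months are counted, or by month 25 (30.11.2024) if 6 months from baseline are counted. Baseline-only subjects may continue to be recruited after that. The cost is a recruitment window for active UC that is 4 to 5 months shorter.
- **Keep 29 months of recruitment.** Move data-collection close, analysis and report to after the last active-UC patient's 6-month visit, that is 30.09.2025 or later. The cost is a later report, since data collection would close at least 4 months later than planned.

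Either way, state whether the 32 and 29 months run from the project start or from the first enrolment. The change is an amendment of dates; no visit or analysis has to be added.

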Appendix 1: Simple Clinical Colitis Activity Index (SCCAI)

Appendix 2: Ulcerative Colitis Endoscopic Index of Severity (UCEIS)

Appendix 3: Schedule Assessments UC

Appendix 4: : Schedule Assessments IBS

Appendix 5: Laboratory tests

Appendix 6: Declaration of Helsinki

Annex 1: Informed Consent and Privacy Forms

Annex 2: eCRF

Annex 3: Budget REBUC

Annex 4: Lista Centri REBUC

Appendix 1

SCCAI: Simple Clinical Colitis Activity Index

Variabile	Punteggio				
	0	1	2	3	4
Numero di scariche diurne	1 - 3	4 - 6	7 - 9	>9	
Numero di scariche notturne		1 - 3	4 - 6		
Urgenza di defecare		di corsa	immediatamente	incontinenza	
Presenza di sangue nelle feci	assente	tracce	occasionale	sempre	
Valutazione clinica globale	molto bene	lievemente al di sotto della normalità	scadente	pessima	terribile
Manifestazioni extraintestinali (1 punto per ciascuna manifestazione)					
Score totale					

Appendix 2

UCEIS: Ulcerative Colitis Endoscopic Index of Severity

Variabile	Punteggio				
	1	2	3	4	5
Pattern vascolare	normale		perdita a chiazze		obliterato
Eritema mucosale	assente		lievemente arrossata		molto arrossata
Superficie mucosale	normale		granulare		nodulare
Edema mucosale	assente		probabile		definito
Presenza di muco-pus	assente		poco		tanto
Presenza di sangue	assente	mucosale	luminale lieve	luminale moderato	luminale severo
Fragilità mucosale	assente	lieve	moderata	severa	molto severa
Fragilità mucosale al contatto	assente		probabile		definita
Presenza di erosioni-ulcere	assenti	presenza di erosioni	presenza di ulcere superficiali	presenza di ulcere profonde	
Estensione di erosioni-ulcere	assente	limitata	sostanziale	estesa	
Score totale					

Appendix 3

Schedule assessments in active UC

	Screening	Baseline	Mandatory follow-up		Optional follow-up	
			3 months	6 months	9 months	12 months
Clinical assessment	X		X	X	X	X
Body Mass Index		X	X	X	X	X
Diagnosis confirmation	X					
Clinical index of activity		X	X	X	X	X
Laboratory analyses		X	X	X		X
Blood sampling		X	X	X		X
Lower endoscopy		X				X
Endoscopic index of activity		X				X
Mucosal sampling		X				X
Histology examination		X				X
Immohistochemistry		X				X
ISH		X				X
Viral load assessment		X				X

Appendix 4

Schedule assessments in UC in remission and IBS

	Screening	Baseline
Clinical assessment	X	
Body Mass Index		X
Diagnosis confirmation	X	
Clinical index of activity		X
Laboratory analyses		X
Blood sampling		X
Lower endoscopy		X
Endoscopic index of activity		X
Mucosal sampling		X
Histology examination		X
Immunohistochemistry		X
ISH		X
Viral load assessment		X

APPENDIX 5: LABORATORY TESTS

WBC
RBC
Hb
MCV
PLT
NEUTROPHILIS
LYMPHOCYTES
SODIUM
POTASSIUM
PROTEINS
ALBUMIN
C REACTIVE PROTEIN
IgG-A-M
anti-EBV IgM/IgG antibodies
Fecal calprotectin

Appendix 6

World Medical Association (WMA) Declaration of Helsinki – Ethical Principles for Medical Research Involving Human Subjects

Adopted by the 18th WMA General Assembly, Helsinki, Finland, June 1964 and amended by the:

29th WMA General Assembly, Tokyo, Japan, October 1975

35th WMA General Assembly, Venice, Italy, October 1983

41st WMA General Assembly, Hong Kong, September 1989

48th WMA General Assembly, Somerset West, Republic of South Africa, October 1996

52nd WMA General Assembly, Edinburgh, Scotland, October 2000

53rd WMA General Assembly, Washington DC, USA, October 2002 (Note of Clarification added)

55th WMA General Assembly, Tokyo, Japan, October 2004 (Note of Clarification added)

59th WMA General Assembly, Seoul, Republic of Korea, October 2008

64th WMA General Assembly, Fortaleza, Brazil, October 2013

Preamble

- The World Medical Association (WMA) has developed the Declaration of Helsinki as a statement of ethical principles for medical research involving human subjects, including research on identifiable human material and data. The Declaration is intended to be read as a whole and each of its constituent paragraphs should be applied with consideration of all other relevant paragraphs.
- Consistent with the mandate of the WMA, the Declaration is addressed primarily to physicians. The WMA encourages others who are involved in medical research involving human subjects to adopt these principles.

General Principles

1. The Declaration of Geneva of the WMA binds the physician with the words, “The health of my patient will be my first consideration,” and the International Code of Medical Ethics declares that, “A physician shall act in the patient’s best interest when providing medical care.”
2. It is the duty of the physician to promote and safeguard the health, well-being and rights of patients, including those who are involved in medical research. The physician’s knowledge and conscience are dedicated to the fulfilment of this duty.
3. Medical progress is based on research that ultimately must include studies involving human subjects.
4. The primary purpose of medical research involving human subjects is to understand the causes, development and effects of diseases and improve preventive, diagnostic and therapeutic interventions (methods, procedures and treatments). Even the best proven interventions must be evaluated continually through research for their safety, effectiveness, efficiency, accessibility and quality.
5. Medical research is subject to ethical standards that promote and ensure respect for all human subjects and protect their health and rights.
6. While the primary purpose of medical research is to generate new knowledge, this goal can never take precedence over the rights and interests of individual research subjects.
7. It is the duty of physicians who are involved in medical research to protect the life, health, dignity, integrity, right to self-determination, privacy, and confidentiality of personal information of research subjects. The responsibility for the protection of research subjects

must always rest with the physician or other health care professionals and never with the research subjects, even though they have given consent.

8. Physicians must consider the ethical, legal and regulatory norms and standards for research involving human subjects in their own countries as well as applicable international norms and standards. No national or international ethical, legal or regulatory requirement should reduce or eliminate any of the protections for research subjects set forth in this Declaration.
9. Medical research should be conducted in a manner that minimises possible harm to the environment.
10. Medical research involving human subjects must be conducted only by individuals with the appropriate ethics and scientific education, training and qualifications. Research on patients or healthy volunteers requires the supervision of a competent and appropriately qualified physician or other health care professional.
11. Groups that are underrepresented in medical research should be provided appropriate access to participation in research.
12. Physicians who combine medical research with medical care should involve their patients in research only to the extent that this is justified by its potential preventive, diagnostic or therapeutic value and if the physician has good reason to believe that participation in the research study will not adversely affect the health of the patients who serve as research subjects.
13. Appropriate compensation and treatment for subjects who are harmed as a result of participating in research must be ensured.

Risks, Burdens and Benefits

1. In medical practice and in medical research, most interventions involve risks and burdens. Medical research involving human subjects may only be conducted if the importance of the objective outweighs the risks and burdens to the research subjects.
2. All medical research involving human subjects must be preceded by careful assessment of predictable risks and burdens to the individuals and groups involved in the research in comparison with foreseeable benefits to them and to other individuals or groups affected by the condition under investigation. Measures to minimise the risks must be implemented. The risks must be continuously monitored, assessed and documented by the researcher.
3. Physicians may not be involved in a research study involving human subjects unless they are confident that the risks have been adequately assessed and can be satisfactorily managed. When the risks are found to outweigh the potential benefits or when there is

conclusive proof of definitive outcomes, physicians must assess whether to continue, modify or immediately stop the study.

Vulnerable Groups and Individuals

1. Some groups and individuals are particularly vulnerable and may have an increased likelihood of being wronged or of incurring additional harm. All vulnerable groups and individuals should receive specifically considered protection.
2. Medical research with a vulnerable group is only justified if the research is responsive to the health needs or priorities of this group and the research cannot be carried out in a non-vulnerable group. In addition, this group should stand to benefit from the knowledge, practices or interventions that result from the research.

Scientific Requirements and Research Protocols

1. Medical research involving human subjects must conform to generally accepted scientific principles, be based on a thorough knowledge of the scientific literature, other relevant sources of information, and adequate laboratory and, as appropriate, animal experimentation. The welfare of animals used for research must be respected.
2. The design and performance of each research study involving human subjects must be clearly described and justified in a research protocol. The protocol should contain a statement of the ethical considerations involved and should indicate how the principles in this Declaration have been addressed. The protocol should include information regarding funding, sponsors, institutional affiliations, potential conflicts of interest, incentives for subjects and information regarding provisions for treating and/or compensating subjects who are harmed as a consequence of participation in the research study. In clinical trials, the protocol must also describe appropriate arrangements for post-trial provisions.

Research Ethics Committees

1. The research protocol must be submitted for consideration, comment, guidance and approval to the concerned research ethics committee before the study begins. This committee must be transparent in its functioning, must be independent of the researcher, the sponsor and any other undue influence and must be duly qualified. It must take into consideration the laws and regulations of the country or countries in which the research is to be performed as well as applicable international norms and standards but these must not be allowed to reduce or eliminate any of the protections for research subjects set forth in this Declaration. The committee must have the right to monitor ongoing studies. The researcher must provide

monitoring information to the committee, especially information about any serious adverse events. No amendment to the protocol may be made without consideration and approval by the committee. After the end of the study, the researchers must submit a final report to the committee containing a summary of the study's findings and conclusions.

Privacy and Confidentiality

1. Every precaution must be taken to protect the privacy of research subjects and the confidentiality of their personal information.

Informed Consent

2. Participation by individuals capable of giving informed consent as subjects in medical research must be voluntary. Although it may be appropriate to consult family members or community leaders, no individual capable of giving informed consent may be enrolled in a research study unless he or she freely agrees.
3. In medical research involving human subjects capable of giving informed consent, each potential subject must be adequately informed of the aims, methods, sources of funding, any possible conflicts of interest, institutional affiliations of the researcher, the anticipated benefits and potential risks of the study and the discomfort it may entail, post-study provisions and any other relevant aspects of the study. The potential subject must be informed of the right to refuse to participate in the study or to withdraw consent to participate at any time without reprisal. Special attention should be given to the specific information needs of individual potential subjects as well as to the methods used to deliver the information. After ensuring that the potential subject has understood the information, the physician or another appropriately qualified individual must then seek the potential subject's freely-given informed consent, preferably in writing. If the consent cannot be expressed in writing, the non-written consent must be formally documented and witnessed. All medical research subjects should be given the option of being informed about the general outcome and results of the study.
4. When seeking informed consent for participation in a research study the physician must be particularly cautious if the potential subject is in a dependent relationship with the physician or may consent under duress. In such situations the informed consent must be sought by an appropriately qualified individual who is completely independent of this relationship.
5. For a potential research subject who is incapable of giving informed consent, the physician must seek informed consent from the legally authorised representative. These individuals must not be included in a research study that has no likelihood of benefit for them unless it is intended to promote the health of the group represented by the potential subject, the

research cannot instead be performed with persons capable of providing informed consent, and the research entails only minimal risk and minimal burden.

6. When a potential research subject who is deemed incapable of giving informed consent is able to give assent to decisions about participation in research, the physician must seek that assent in addition to the consent of the legally authorised representative. The potential subject's dissent should be respected.
7. Research involving subjects who are physically or mentally incapable of giving consent, for example, unconscious patients, may be done only if the physical or mental condition that prevents giving informed consent is a necessary characteristic of the research group. In such circumstances the physician must seek informed consent from the legally authorised representative. If no such representative is available and if the research cannot be delayed, the study may proceed without informed consent provided that the specific reasons for involving subjects with a condition that renders them unable to give informed consent have been stated in the research protocol and the study has been approved by a research ethics committee. Consent to remain in the research must be obtained as soon as possible from the subject or a legally authorised representative.
8. The physician must fully inform the patient which aspects of their care are related to the research. The refusal of a patient to participate in a study or the patient's decision to withdraw from the study must never adversely affect the patient-physician relationship.
9. For medical research using identifiable human material or data, such as research on material or data contained in biobanks or similar repositories, physicians must seek informed consent for its collection, storage and/or reuse. There may be exceptional situations where consent would be impossible or impracticable to obtain for such research. In such situations the research may be done only after consideration and approval of a research ethics committee.

Use of Placebo

1. The benefits, risks, burdens and effectiveness of a new intervention must be tested against those of the best proven intervention(s), except in the following circumstances: Where no proven intervention exists, the use of placebo, or no intervention, is acceptable; or Where for compelling and scientifically sound methodological reasons the use of any intervention less effective than the best proven one, the use of placebo, or no intervention is necessary to determine the efficacy or safety of an intervention and the patients who receive any intervention less effective than the best proven one, placebo, or no intervention will not be subject to additional risks of serious or irreversible harm as a result of not receiving the best proven intervention. Extreme care must be taken to avoid abuse of this option.

Post-Trial Provisions

1. In advance of a clinical trial, sponsors, researchers and host country governments should make provisions for post-trial access for all participants who still need an intervention identified as beneficial in the trial. This information must also be disclosed to participants during the informed consent process.

Research Registration and Publication and Dissemination of Results

2. Every research study involving human subjects must be registered in a publicly accessible database before recruitment of the first subject.
3. Researchers, authors, sponsors, editors and publishers all have ethical obligations with regard to the publication and dissemination of the results of research. Researchers have a duty to make publicly available the results of their research on human subjects and are accountable for the completeness and accuracy of their reports. All parties should adhere to accepted guidelines for ethical reporting. Negative and inconclusive as well as positive results must be published or otherwise made publicly available. Sources of funding, institutional affiliations and conflicts of interest must be declared in the publication. Reports of research not in accordance with the principles of this Declaration should not be accepted for publication.

Unproven Interventions in Clinical Practice

1. In the treatment of an individual patient, where proven interventions do not exist or other known interventions have been ineffective, the physician, after seeking expert advice, with informed consent from the patient or a legally authorised representative, may use an unproven intervention if in the physician's judgment it offers hope of saving life, re-establishing health or alleviating suffering. This intervention should subsequently be made the object of research, designed to evaluate its safety and efficacy. In all cases, new information must be recorded and, where appropriate, made publicly available.
